### 108 A1 Study Abstract

109 COVID-19 has now infected over 33 million people in the United States and approximately 185 million worldwide. Of those, an estimated 85% have reported either 110 a new clinical diagnosis or subjective onset of olfactory dysfunction. While most 111 patients will recover their sense of smell within 7-14 days, others may not return to their 112 113 baseline function for months or at all. Viral infections that target the upper respiratory 114 system, such as COVID-19, often leave patients with diminished olfaction. This new-115 onset anosmia, hyposmia, and parosmia is theorized to be caused by damage to sensory 116 neurons following viral insult. Unfortunately, there is no treatment for post-COVID 117 olfactory dysfunction. Most patients are recommended to perform olfactory training with essential oils, but the evidence base to support this recommendation is not firm. Thus, 118 119 there is a very big need for effective treatments for patients suffering from post-COVID 120 olfactory dysfunction.

121

122 One potential therapy is gabapentin. Used as an antiepileptic and now first-line

123 medication for the treatment of diabetic neuropathy, gabapentin is known for reducing

124 pain secondary to diabetic neuropathy and post-herpetic neuralgia. Gabapentin works

125 mainly on voltage-gated calcium channels (VGCC) with an ability to cross the basement

126 membrane, a trait important for an antiepileptic. The  $\alpha 2\delta 2$  subunit of VGCCs, with

127 increased expression in corticospinal neurons, has been associated with loss of regrowth

128 after spinal injuries. The  $\alpha 2\delta 2$  blockage by gabapentin can allow increased nerve

regeneration and return of function. Inhibition of the  $\alpha 2\delta 2$  subunit on VGCCs may allow

130 nerves to regenerate more rapidly than physiologically normal. This study will evaluate 131 the efficacy of gabapentin for olfactory dysfunction (anosmia, hyposmia, parosmia) in

132 post-COVID-19 patients.

### 133 A2 Primary Hypothesis

We hypothesize that oral gabapentin will be more effective than placebo for COVID-19-related olfactory dysfunction (OD) improvement.

### 136 A3 Purpose of the Study Protocol

137 This study will evaluate the efficacy of gabapentin for olfactory dysfunction (anosmia,

- 138 hyposmia, parosmia) in post-COVID-19 patients.
- 139

140	B	Background		

### 142 **B1 Prior Literature and Studies**

The SARS-CoV-2 virus, has infected an estimated 78 million in the United States with ~85% of patients reporting some form of olfactory dysfunction. More recent studies have shown an increased prevalence of olfactory change reported in women over men and in Western countries when compared to Eastern countries. Moreover, the percentage of patients with post-COVID-19 olfactory dysfunction is thought to be underreported as patients need to individually report the symptom to their physician for it to be recorded.

150

151 Evidence has emerged to explain the pathophysiology of COVID-19 and its mechanism 152 of action on neurosensory pathways. Research suggests that COVID-19 affects two genes 153 commonly found in the human respiratory system, ACE2 and TMPRSS2.. ACE2, 154 commonly associated with the renin-angiotensin-aldosterone system, has another role as 155 a receptor protein on cell surfaces - a receptor proven vital for SARS-CoV-2 to enter respiratory cells. Similarly, TMPRSS2 also plays a role in SARS-CoV-2 entry into cells 156 and both genes are expressed in neuronal support cells. ACE2 and TMPRSS2 are found 157 158 only in support cells and not neurons. The support cells, such as sustentacular cells, 159 degenerate and are unable to sustain neurons. This lack of neuronal stability is what 160 likely causes the temporary neurosensory loss seen in post-COVID-19 patients. However, evidence is now also supporting the theory that COVID-19-related olfactory dysfunction 161 162 may be due to direct damage to olfactory receptor neurons (ORNs) as well, which would 163 increase recovery time as neurons regenerate more slowly. Previous strains of human 164 coronavirus have also been proven to target ORNs causing olfactory dysfunction but 165 whether this direct damage to neurons is related to ACE2 and TMPRSS2 has yet to be determined. 166

167

168 Patients who do recover their sense of smell after infection tend to notice improvement in 169 just weeks, paralleling the rapid recovery rate of support cells. Those with lingering 170 olfactory dysfunction either return to new normalcy in months instead of weeks or have 171 yet to return to baseline. Some patients report a return of smell followed shortly by new 172 smell distortion. This observation of differing recovery rates supports the theory that 173 SARS-CoV-2 also damages olfactory receptor neurons directly leading to longer 174 recovery times. Research has demonstrated the possible utility in olfactory training, a therapy thought to encourage neuroplasticity via repeat exposure to odors. However, 175 176 the evidence to support this treatment is not universally accepted and pharmacotherapy 177 options for post-COVID-19 olfactory dysfunction are still being explored; one potential 178 therapy is gabapentin.

179

Gabapentin is an antiepileptic medication now used as first-line therapy for diabetic
 neuropathy and herpetic neuralgia. Gabapentin works by binding to VGCCs, which play

182 an important role in neuronal synaptic transmission. More specifically, gabapentin binds

183 to  $\alpha_2\delta$  isoforms which have been associated with neuropathic pain. The postsynaptic  $\alpha_2\delta 1$ 

184 subunit promotes spinogenesis, the development of neuronal dendritic spines, while the

185  $\alpha_2 \delta^2$  works as a suppressor of axonal regeneration. Gabapentin functions as an inhibitor

186 of the  $\alpha_2 \delta 2$  subunit and therefore blocks the suppression of axonal regeneration leading to

187 increased neuronal regeneration and function. The medication is effective in the treatment

188 of chronic pain and burning mouth syndrome (BMS). The mode of action is thought to be

189 primarily due to the fact that gabapentin is highly lipophilic and can enter the central

nervous system (CNS) and iad in neuron regeneration. For these reasons, gabapentin is 190

- 191 thought to have the potential to improve post-COVID-19 olfactory dysfunction caused by
- 192 neuronal damage. Our study will investigate the efficacy of gabapentin to increase
- 193 recovery of olfactory dysfunction secondary to post-COVID-19 infection.
- 194

#### 195 **B2** Rationale for this Study

**Study Objectives** 

196 Olfactory dysfunction is a major symptom of SARS-CoV-2 affecting up to 80% of 197 infected individuals. While most have a return to normal olfactory function in weeks, 198 some may not see full improvement for months and a small percentage may not recover 199 function and suffer long-term physical limitation and functional impairment. This 200 placebo-controlled, double-blinded pilot RCT will evaluate the efficacy of oral 201 gabapentin to improve chronic (>3 months) olfactory dysfunction secondary to COVID-202 19 infection. This study will provide data on the efficacy of gabapentin for the treatment of OD.

203 204

205

С

206

#### 207 *C1* **Primary** Aim

208 To evaluate the efficacy of oral gabapentin on improvement of olfactory dysfunction in 209 patients with post-COVID-19 anosmia, hyposmia, or parosmia. Participants will receive a 210 maximum of 14weeks of either gabapentin or placebo with the first four weeks serving as 211 a titration phase and the last two weeks serving as a taper-down period.

212 *C2* Secondary Aim

213 Describe the adverse effects of gabapentin. All participants will be monitored for adverse 214 effects throughout the study.

#### 215 С3 **Rationale for the Selection of Outcome Measures**

### 216

### 217 **Primary Outcome:**

218 Clinical Global Impression of Improvement Scale (CGI-I). The response rate is 219 defined as the number of participants self-reporting minimal change or larger on 220 the Clinical Global Impression of Improvement Scale (CGI-I) scale, divided by 221 the number of participants in each group. The CGI-Improvement is a self-222 reported scale of improvement ranging from 1 to 7 (1 is Very Much Improved, 7 223 is Very Much Worsened) and will be measured after completing 8 weeks of the 224 fixed, highest-tolerable dose. Each rating is well defined to maximize accuracy. 225 Participants reporting 3 as Minimally Improved, 2 as Much Improved, or 1 as Very 226 Much Improved in the CGI-I will be deemed responders to treatment, and the 227 number of responders to non-responders will be compared between the two arms -228 CGI-Severity (CGI-S) and CGI-Improvement (CGI-I).

229	
230	
231	Secondary Outcomes:
232	1. CGI-Severity. The CGI-Severity scale ranges from 1 to 7, where 1 is normal
233	function and 7 is complete anosmia. This assessment will provide subjective data
234	on patients' baseline olfactory function prior to beginning the trial, after 8-week
235	Fixed-Dose period, and 4 weeks after completion of Taper-Down phase.
236	2. CGI-Improvement. The CGI Improvement will also be administered 4 weeks
237	after completion of Taper-Down phase which same analysis as described above.
238	3. University of Pennsylvania Smell Identification Test (UPSIT).  The UPSIT is
239	composed of 40 strips of microencapsulated odorants, which are present on the
240	bottom of each page, just below a four-alternative multiple-choice question. For a
241	given item, the patient releases an odor by scratching the microencapsulated pad
242	with a pencil tip, smells the pad, and indicates the odor quality from four
243	alternatives. Even if no smell is perceived, a response is required (i.e., the test is
244	forced-choice). The subject's total correct score out of the 40 items is
245	determined. 
246	The total UPSIT score can range from 0 to 40 and scores are interpreted as the
247	level of absolute smell function (i.e., normosmia, mild hyposmia, moderate
248	hyposmia, severe hyposmia, and anosmia), using the age- and sex-related
249	normative classification system described in the UPSIT manual (Table 1) The
250	minimal clinically important difference in UPSIT score is 4.

Disease Classification Based on UPSIT		Women	Men
Normosmia		>34	>33
Hyposmia			
	Mild	31-34	30-33
	Moderate	26-30	26-29
	Severe	19	-25
Anosmia		6-	18
Malingering		5	5

- 251Malingering≤ 52524.Olfactory Dysfunction Outcomes Rating (ODOR). The ODOR questionnaire is a25328-item disease-specific health status survey to assess the physical problems,254functional impairments, and emotional consequences secondary to olfactory255dysfunction. ODOR was developed and validated by [name] and colleagues256in the Clinical Outcomes Research Office at Washington University.
- 257 5. NASAL-7. NASAL-7 is a simple diagnostic tool for olfactory dysfunction that is 258 based on commonly found household items and can be used by adults who 259 suspect olfactory dysfunction. The NASAL-7 was developed by [name] and 260 colleagues in the Clinical Outcomes Research Office. The NASAL-7, contains 7 261 household items with each item scored as 0 for 'Cannot Smell', 1 for 'Smells Less 262 Strong/Different Than Normal', and 2 for 'Smells Normal', for a total possible 263 score ranging from 0-14. The following four categories of olfactory function 264 were defined based on NASAL-7 score: anosmia (score 0-4), severe dysfunction (score 5-7), mild dysfunction (score 8-10), and normosmia (score 11-14). 265
- 6. Clinical Global Impression-Severity Scale for Parosmics (CGI-P). The CGI-P
  Scale is a global rating of parosmia and the single global rating ranges from 1-5,
  where 1 is No Distortion, 2 is Mild Distortion, 3 is Moderate Distortion, 4 is
  Mostly Distorted, and 5 is Complete Distortion. The response on the CGI-P will

270 271 272	provide information on the patient's perceived severity of the distortion of their smell.
273	D Investigational Agent
274	
275	D1 Preclinical Data
276	Gabapentin is an antiepileptic medication now used as first-line therapy for diabetic
277	neuropathy and herpetic neuralgia. Gabapentin works by binding to voltage-gated
278	calcium channels (VGCCs), which play an important role in neuronal synaptic
279	transmission. More specifically, gabapentin binds to $\alpha_2\delta$ isoforms which have been
280	associated with neuropathic pain.
281	
282	The $\alpha 2\delta 2$ subunit of VGCCs, with increased expression in corticospinal neurons, has
283	been associated with loss of regrowth after spinal injuries. The postsynaptic $\alpha_2 \delta 1$ subunit
284	promotes spinogenesis, the development of neuronal dendritic spines, while the $\alpha_2 \delta 2$

works as a suppressor of axonal regeneration. The  $\alpha 2\delta 2$  blockage by gabapentin can allow increased nerve regeneration and return of function. Inhibition of the  $\alpha 2\delta 2$  subunit

on VGCCs may allow nerves to regenerate more rapidly than physiologically normal.

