### 443 **2.g** When and How to Withdraw Subjects

444 A participant can withdraw consent for the study at any time. Participants will be allowed 445 to end participation in the study at any point should they desire. If a participant must be 446 withdrawn due to a drug-related serious adverse event, then blind will be broken and, if 447 on gabapentin, drug withdrawal will be tapered or completely stopped based on the 448 clinical judgement of the PI. All participants will have an exit interview to ascertain any 449 adverse effects and discuss the reason for ending participation. The study team will 450 follow them for safety reasons up to 30 days after stopping use of the study drug.

451

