### 587 Gabapentin (300 mg pill) Titration Schedule

588

586

589 If at any point during the Titration Period, the participant wishes to discontinue 590 the medication for any reason, they will be instructed to follow the taper down schedule 591 (see below) in order to safely stop the medication. The participant will be informed that 592 any abrupt stoppage of gabapentin could cause serious adverse effects.

Participants will be contacted by telephone or video call by the Research Assistant
(RA) at the end of Titration period. The purpose of this call will be to query the
participants about adverse effects. Participants will be provided with a paper calendar
and asked to maintain diaries of olfactory and taste symptoms and adverse effects
possibly related to the intervention.

598 Participants will not complete any forms at the completion of Titration period.599 Instead, they will proceed directly to Fixed-Dose Period.

### 600 601

Fixed-Dose Period: duration 8 weeks

602During the Fixed-Dose period, participant's dose will remain at their maximum tolerated603dosage established during the Titration phase. The study drug will be distributed in eight604separate vials representing the eight weeks of the Fixed-Dose period. The RA will605contact the participants at the end of Week 4 to administer the blind assessment using606REDCap (survey titled: "Blind Assessment"). Participants will complete the following607forms after completing the Fixed-Dose Period (survey titled: "FixedDoseSurvey"):

- 608
- 609 1.) Clinical Global Impression of Severity Scale (CGI-S).

610 2.) Clinical Global Impression of Improvement Scale (CGI-I)

- 611 3.) University of Pennsylvania Smell Identification Test (UPSIT)
- 612 4.) Olfactory Dysfunction Outcomes Rating (ODOR)
- 613 5.) *NASAL-7*
- 6.) *Clinical Global Impression-Severity Scale for Parosmics (CGI-P)*
- 615 7.) Adverse Event assessment
- 616 8.) Compliance
- 617

618 *Adverse events*. Any unintentional or unfavorable clinical sign or symptom, any new

619 illness or disease or the deterioration of existing disease or illness, or any clinically

620 significant deterioration in any laboratory assessments or clinical tests while participating

621 in this study will be captured. The study coordinator will contact participants virtually to

622 answer questions and assess adverse effects after Titration period, Fixed-Dose period,

- 623 and 4 weeks after Taper.
- 624

- 625 Taper Down: maximum duration 2 weeks

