### 667 i Investigator only

668 The PI and the study team will be monitoring patients for any safety concerns, such as 669 SAE or UAE, in real time for the duration of the 18-week study. In addition, participants 670 will be specifically asked about any adverse events after the Fixed-Dose period via 671 REDCap. Participants will be able to get in touch with a member of the study team 24/7via phone or pager for the duration of the 18-week clinical trial. The study biostatistician 672 673 will hold the randomization codes and remain blinded to the intervention assignment. In 674 the event of an SAE or UAE in which the blind needs to be broken, the Research 675 Pharmacist will be contacted by the PI or a member of the study team. The participant 676 will receive appropriate care and will be removed from the trial. A description of the 677 event will be included in the report of adverse events for the clinical study. 678

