## 766 F4 Study Outcome Measurements and Ascertainment

Participants will complete an assessment of blind after completion of 4 weeks of
the 8-week Fixed-Dose period using REDCap (survey titled: "Blind Assessment")

Participants will also complete the following forms using REDCap (survey titled
"FixedDoseSurvey") after completing the 8-week Fixed-Dose Period:

772 773

1.) Clinical Global Impression of Severity Scale (CGI-S).

7742.) Clinical Global Impression of Improvement Scale (CGI-I)

- 7753.) University of Pennsylvania Smell Identification Test (UPSIT)
- 4.) Olfactory Dysfunction Outcomes Rating (ODOR)
- 777 5.) *NASAL-7* 
  - 6.) Clinical Global Impression-Severity Scale for Parosmics (CGI-P)
- 779 7.) Adverse Event assessment
- 780 8.) Compliance
- 781

782	Participants will also complete the following forms using REDCap (survey titled		
783	FinalSurvey) 4 weeks after completing the Taper Period.		
784	1)	Clinical Global Impression of Severity Scale (CGI-S).	
785	2)	Clinical Global Impression of Improvement Scale (CGI-I)	
786	3)	University of Pennsylvania Smell Identification Test (UPSIT)	
787	4)	Olfactory Dysfunction Outcomes Rating (ODOR)	
788	5)	NASAL-7	
789	6)	Clinical Global Impression-Severity Scale for Parosmics (CGI-P)	
790			
791			

792 G Statistical Plan

793

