### 794 G1 Sample Size Determination and Power

795 To date there have been no studies investigating efficacy of gabapentin in COVID-19 796 related olfactory dysfunction. Due to the lack of preliminary data and effect size, 797 estimates of the sample size for this study will be determined based on feasibility. For 798 this pilot study, we plan to enroll 60 subjects. The sample size of 60 subjects is feasible 799 given the incidence of COVID-19 cases in Missouri and considering a conservative 800 estimate of a 10% rate of permanent olfactory dysfunction among those (~50%) who 801 experience olfactory dysfunction as one of the presenting symptoms. Using a 33% drop 802 out rate, we estimate that the sample size of 60 subjects randomized in a balanced way 803 between the two treatment groups will provide us with 40 evaluable cases. A previous 804 study exploring a different treatment for COVID-19 related anosmia in our lab showed 805 that 30% of the participants randomized to placebo reported improvement at the end of 806 the trial as compared to baseline. We aim to observe a 25% difference in the response 807 rate between gabapentin and placebo groups. Assuming that this will be the response rate 808 in the placebo group of our trial, the sample size of 20 subjects per group will provide us 809 with a 95% Confidence Interval -5% to 55% around the desired proportion difference of 810 25% between gabapentin and placebo groups.

811

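### Once a participant ends participation no CGI-I is collected and earlier data are dropped, so about 20 of 60 would lack the primary rating in an analysis described as intention-to-treat

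*Combined protocol and SAP*

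**What the plan says.** **When CGI-I is taken.** C3 defines the primary outcome as a 1-to-7 self-rating on which 7 "is Very Much Worsened) and will be measured after completing 8 weeks of the" fixed, highest tolerable dose. "Participants reporting 3 as Minimally Improved, 2 as Much Improved, or 1 as Very" Much Improved count as responders, and the stated denominator is the number of participants in each group. The second rating is a secondary outcome: "2. CGI-Improvement. The CGI Improvement will also be administered 4 weeks" after the taper ends. F2 and F4 agree, listing CGI-I in FixedDoseSurvey and FinalSurvey and nowhere else.

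**Contacts without CGI-I.** After titration there is a call about adverse effects, but "Participants will not complete any forms at the completion of Titration period" (F2). Midway through fixed dosing there is an online survey on blinding: "Participants will complete an assessment of blind after completion of 4 weeks of" the Fixed-Dose period (F4). Two-weekly check-ins (E3 3.e) cover questions and adherence.

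**What happens to leavers.** E2 2.g says: "All participants will have an exit interview to ascertain any" adverse effects and to discuss why the person is leaving; no CGI-I is listed. E2 2.h then limits data to that interview and whatever was collected before, allows no other follow-up, and states that the earlier data are not analysed. Under F3 3.a i, a participant whose blind is broken for a serious or unexpected event "will receive appropriate care and will be removed from the trial".

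**What the analysis expects.** G1: "Using a 33% drop" out rate, 60 enrolled become 40 evaluable. G3 calls the primary analysis intention-to-treat, in the groups first assigned. G4 assumes data are missing at random and rules out any computational adjustment.

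**The concern.** A third of the sample is planned to be lost to the primary outcome, and the main cause is a rule on data collection. Under 2.h a person who leaves before the end of fixed dosing is never asked the primary question. Read literally, 2.h also discards the rating of someone who leaves during taper or follow-up, after the primary survey.

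The active arm is titrated to the highest tolerable dose against an inert placebo. Leaving for intolerance, or for lack of benefit, is therefore plausible and could differ by arm. In that case the responder difference among those who remain is not the difference among those randomised. G4's missing-at-random assumption could not be examined either, because leavers would contribute no efficacy rating after baseline. No analysis after the trial can supply ratings that were never requested.

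**Working it through.** **Inputs.** From G1: 60 enrolled, 33% dropout, 40 evaluable, placebo response 30%, target difference 25 points (so 55% on gabapentin), stated 95% CI -5% to 55%. G1 randomises evenly, giving 30 per arm. Two assumptions are mine: leavers split evenly, 10 per arm, and the observed rates equal the planning values, 6/20 and 11/20.

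**Step 1: reproduce the plan's figures.**
- Evaluable: 60 × (1 - 0.33) = 40.2, or 40, which is 20 per arm.
- Unpooled Wald interval: half-width = 1.96 × √(0.30×0.70/20 + 0.55×0.45/20) = 1.96 × √0.022875 = 29.6 points. Hence 25 ± 29.6 = -4.6% to 54.6%, matching the stated -5% to 55%.

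That interval describes the 40 evaluable participants only.

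**Step 2: bound the difference over all 60 randomised.**
- Worst case (gabapentin leavers all non-responders, placebo leavers all responders): 11/30 - 16/30 = -16.7 points.
- Best case (the reverse): 21/30 - 6/30 = +50.0 points.
- All leavers counted as non-responders: 11/30 - 6/30 = +16.7 points.

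The range is 50.0 + 16.7 = 66.7 points.

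**Step 3: what continued collection would gain.** The documents say neither when people leave nor how many would answer a later survey, so the captured share is shown as a range. With n rated and m = 30 - n missing per arm:
- half-width = 1.96 × √(0.4575/n), where 0.4575 = 0.30×0.70 + 0.55×0.45
- worst = (0.55n - 0.30n - m)/30
- best = (0.55n + m - 0.30n)/30

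| Leavers captured (assumed) | Rated per arm | 95% CI | Worst to best over 60 | Width |
|---|---|---|---|---|
| 0% | 20 | -4.6% to 54.6% | -16.7 to +50.0 | 67 |
| 50% | 25 | -1.5% to 51.5% | +4.2 to +37.5 | 33 |
| 100% | 30 | 0.8% to 49.2% | +25 | 0 |

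The table keeps the rates at 30% and 55% among captured leavers. It applies only to ratings made at the scheduled end of fixed dosing, which is week 12 with a full 4-week titration (4 + 8). A rating given at exit or midway does not fix the week-12 response and does not narrow these bounds.

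**The case against.** **The sparse schedule is deliberate.** G4 aims to limit missing data by keeping assessments few and simple. This stands against adding a mid-period CGI-I, which is best left optional. It does not stand against sending an existing survey to people who would otherwise receive none.

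**The plan already handles leavers.** C3 divides by all participants in the group and G3 says intention-to-treat, so leavers could be read as non-responders, giving +16.7 points. But 2.h excludes their data and G1 counts only 40 as evaluable, so the passages conflict. Nor would that reading supply the missing ratings.

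**Two stronger readings are tempting and go too far.** A reader might infer that anyone who stops the drug is denied the primary survey. The documents do not say so: 2.h applies to those who have ended participation, 2.f to withdrawal from the whole study, and only removal after serious events is explicit. For someone who stops only the drug, the text is silent. A reader might also infer that the exit interview is confined to adverse effects and the reason for leaving. 2.g does not say that it is, and F2 gives the final visit an exit-interview label with CGI-I among its forms. That visit, however, is timed 4 weeks after taper, so it does not show that early leavers are rated.

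**More ratings alone would solve it.** They would not. Under 2.h they would be discarded, and under G4 no method could use them.

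**This is a small pilot.** True, and G1 makes no power claim. At 50% capture the interval moves about 3 points at each end and still includes zero. The case rests on selection more than on precision.

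**Conclusion.** The point holds as a conflict between the data-collection rule in 2.h and the intention-to-treat statement in G3, in a plan that rates the primary outcome once on treatment. At the planned dropout, about 20 of 60 would have no usable primary rating, and the difference over all randomised would be bounded only by -17 and +50 points. Those bounds are extremes, not a forecast. They rest on the planning rates, an even split of leavers, and reading all of G1's 33% as lacking a primary rating, which is how G1 itself counts them. The benefit of the change depends on a capture rate that the documents do not give. The change is worth making because collection cannot be repaired after the trial.

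**What to change.** 1. **Amend E2 2.h.** State that stopping the drug or being removed does not end outcome collection. Send FixedDoseSurvey (at least CGI-I and CGI-S) on the originally scheduled end-of-Fixed-Dose date to everyone who has not refused contact, and include these ratings in the intention-to-treat primary analysis. Because titration length varies, define that date in advance for people who leave early, and align the timing wording in C3.
2. **Delete the rule in 2.h that withdrawn participants' data are not used.** This removes the conflict with G3.
3. **Add the one-item CGI-I to the leavers' exit interview** as an auxiliary value for a pre-specified sensitivity analysis, and edit G4 to permit it. It does not replace the week-12 rating.
4. **Optional:** a CGI-I item in the mid-Fixed-Dose survey. If it is placed before the treatment guess, it may prompt guesses based on perceived benefit.

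**Cost.** One online survey for leavers, one interview item, and matching edits to C3, 2.h and G4. No visit is added and dosing is untouched. Some ratings will be made off drug, so the result is a treatment-policy effect. That is consistent with the intention-to-treat analysis already promised, but the plan should say so.
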